Enrollment	Point/time of patient entry into the study; the point at which informed consent must be obtained (i.e. prior to starting any of the procedures described in the protocol)
Investigational drug	The study drug whose properties are being tested in the study; this definition is consistent with US CFR 21 Section 312.3 and is synonymous with “investigational new drug.”
Medication pack number	A unique identifier on the label of each investigational drug package
Patient ID	A unique number assigned to each patient upon signing the informed consent
Randomization number	A unique identifier assigned to each randomized patient, corresponding to a specific treatment arm assignment
Study drug	Any single drug or combination of drugs administered to the patient as part of the required study procedures; includes investigational drug(s), placebo/comparator active drug run-ins or background therapy
Study Treatment Discontinuation (TD)	When the patient permanently stops taking study treatment prior to the defined study treatment completion date
Variable	A measured value or assessed response that is determined in specific assessments and used in data analysis to evaluate the drug being tested in the study
Withdrawal of consent (WoC)	Withdrawal of consent from the study is defined as when a patient does not want to participate in the study any longer, and does not want any further visits or assessments, and does not want any further study related contact, and does not allow analysis of already obtained biologic material

Amendment 3

Amendment rationale

- The rationale for this amendment is to reflect the changes in the Core protocol (CZOL446H2337) v05 which has been amended [REDACTED] to provide a Risk Benefit statement ([Section 3.6](#)), and allow more countries to apply the contraceptive wording originally provided for UK sites only.
 - The introduction ([Section 1](#)) has been revised with more recent references that reflect the increase in knowledge of childhood osteoporosis since the protocol was first proposed.
 - The investigational plan ([Section 3](#)) and statistical sections ([Section 9](#)) have been clarified.
 - In addition, the DMC concerns regarding potential for transient symptomatic hypocalcemia after first infusion are addressed by adding additional calcium supplementation at the recommended daily allowance (RDA) for age in [Table 5-1](#) for up to 10 days around time of infusion (in line with Institutional clinical practice guidelines).

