 - [Table 5-1](#) has been revised in line with the current minimum RDAs for vitamin D and calcium from the Institute of Medicine.
 - Visit 9 for Group 1 is now defined as up to 10 months after Visit 5 (month 6) of the Core study, to allow patients who are deteriorating at the time of the second infusion during the Core study to enter the Extension study rather than be treated off-label.
 - This amendment includes clarification of the list of eligible medical conditions other than chronic rheumatologic conditions or inflammatory bowel disease or Duchenne muscular dystrophy (DMD) already specified previously. These additional conditions are listed in [Appendix 6](#) and the exclusion criteria for Group 2 have been revised to address these as follows:
 - Due to the inclusion of some of these additional medical conditions, e.g. nephrotic syndrome, the exclusion criterion of renal impairment previously defined as an estimated glomerular filtration rate (GFR) < 35 mL/min/1.73 m² at screening has been increased to normal renal function defined as < 60 mL/min/1.73 m² based on the Schwartz formula at Visit 8 (Group 1) or Visit 8A (Group 2).
 - Schwartz formula has been added under [Section 6.5.4.2](#)
 - In addition ‘serious renal disease’ in DMD has been removed as this is included under the GFR exclusion criterion.
 - In DMD patients, chronic muscle breakdown results in elevated aspartate aminotransferase (AST) and alanine aminotransferase (ALT) (frequently higher than 10 fold); hence total bilirubin and gamma-glutamyl transpeptidase (GGT) have been added as additional markers to detect any potential liver toxicity.

- The exclusion criterion ‘symptomatic cardiac abnormality’ in DMD has been redefined because other conditions or concomitant medications, including glucocorticoids can contribute to cardiac disease: Uncontrolled symptoms of cardiac failure or arrhythmia.
- Serum 25-hydroxy vitamin D concentrations have been revised to the currently accepted definition of normal i.e. < 20 ng/mL or < 50 nmol/L at Visit 8A for Group 2.
- The blood volume required ([Appendix 7](#)) for the analysis of specialized bone markers has been reduced from 8.5 mL to 3 mL.
- The local serum creatinine before the second infusion of zoledronic acid has been removed because of the need for normal renal function as an eligibility criterion. Renal function is reviewed centrally before and 10 days after each infusion.

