- Inconsistencies have been corrected within the protocol and across supporting documents especially with respect to Serious Adverse Event/Adverse Event reporting in Group 2 and central laboratory analyses.
- In this 12 month study, visit windows have been removed and replaced with a requirement to perform the visit as close to the designated day as possible. For Group 2 only, the time between Visit 8A and Visit 9 should be as close to 28 days as possible, but cannot be longer than 8 weeks.

The latest Novartis protocol template has been used to aid the reader in navigating the protocol and more some procedures have been revised in line with our current processes.

Status of the study as of 10-May-2016:

Twelve (12) patients have been enrolled onto this study, all were enrolled into Group 1; the proposed changes will have no impact on the interpretation of the data.

Changes to the protocol

Changes to specific sections of the protocol are shown by track changes in the track changes version of the protocol using ~~strike through red font for deletions~~, and red underlined for insertion.

[figure not shown]
A copy of this amended protocol will be sent to the Institutional Review Board (IRBs)/Independent Ethics Committee (IECs) and Health Authorities.

The changes herein affect the Informed Consent. Sites are required to update and submit for approval a revised Informed Consent that takes into account the changes described in this protocol amendment.

[figure not shown]
Summary of previous amendments:

Amendment 2

The rationale for this amendment (dated 15-Jan-2014) was to reflect the changes in the Core (CZOL446H2337) protocol v04 which extended the study population to include subjects with

underlying conditions other than chronic inflammatory disorders e.g. Duchenne muscular dystrophy (DMD).

- Include (Group 2): patients not eligible to enroll into the Core study because of clinically significant back pain (significant symptoms) from vertebral fracture and the preexisting clinical care at the Investigator's site is to treat this type of patient with a bisphosphonate. Therefore two Baselines are used in the study:
 - Baseline 1: First visit of the Core for Group 1
 - Baseline 2: First visit of the Extension for Group 2.
- Align with the Core study changes in the Inclusion/Exclusion criteria:
 - Relax the LS BMD Z-score inclusion criteria from -1.0 to -0.5 or worse.

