3.1 Study design

This study is a 1-year open-label extension to the CZOL446H2337 Core study. The study uses a single treatment arm (zoledronic acid); there will be no placebo or active control group. All patients will be osteoporotic children and adolescents receiving GC therapy of any duration within the 12 months preceding Baseline (Visit 1 of the Core study for Group 1; Visit 8A of this study for Group 2). All patients must manifest a LS-BMD Z-score of -0.5 or worse and have evidence of low impact/fragility fracture at either the Baseline of the Core Study (Group 1) or this study (Group 2).

Group 1: Patients who have received at least one dose of study drug and who have completed the Core study and who meet the inclusion/exclusion criteria for this Extension study will be eligible to enroll. The final visit of the Core study (Visit 8) will serve as the first (screening) visit for the Extension study. At Visit 8A, which may take place on the same day as Visit 8, patients will complete additional screening assessments for the Extension study. Patients will return at Visit 9 (which can also be on the same day as Visit 8 of the Core study) and all patients will receive zoledronic acid. The allowed window for Visit 9 is up to 10 months after Visit 5 (month 6) of the Core study (up to 4 months after Visit 8 of the Core study). Note that Visit 8 and Visit 9 can be combined if the patients or parents or legal guardians have provided informed consent to enter into the Extension study prior to Visit 8 and undergone the appropriate screening procedures as outlined in [Section 6](#). Central labs from Visit 8 will be utilized for the Extension Visit 9, provided the lab samples have been collected within 30 days prior to the Visit 9 infusion. Otherwise, the labs must be redrawn and the results reviewed for eligibility, prior to infusion at Visit 9. The DXA scans (hip, spine and distal femur) from Visit 8 will be used for the extension Visit 9 provided the DXAs have been obtained within 3 months of the Visit 9 infusion; otherwise, the DXA scans must be repeated at Visit 9.

Group 2: Children, male or female, 5 to 17 years of age who otherwise met the inclusion criteria for entry into the Core study but did not complete screening on the Core study because of clinically significant back pain due to vertebral fracture and the preexisting clinical care at the Investigator's site is to treat this type of patient with a bisphosphonate.

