### General considerations

#### Baseline definition

Unless otherwise specified, the following general rules will be applied for defining baseline.

- Core baseline: core baseline is defined as the last non-missing measurement on or prior to the date of first study drug infusion in core study.

- Extension baseline: extension baseline is defined as the last non-missing measurement on or prior to the date of first study drug infusion in the extension study. If no extension assessments are available on or prior to the first drug infusion in the extension study, the last assessment in core study will be used instead.

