### **Laboratory parameters**

The summary of laboratory evaluations will be presented with respect to three groups of laboratory tests (hematology, serum chemistry, and urinalysis).

- Hematology parameters: hemoglobin, hematocrit, platelet count, red blood cell count (RBC), mean cell volume (MCV), mean cell hemoglobin concentration (MCHC), RBC morphology, white blood cell count (WBC) and differential white blood cell counts.
- Serum chemistry parameters: non-fasting glucose, creatinine, serum urea, uric acid, total protein, SGOT (AST), SGPT (ALT), alkaline phosphatase, sodium, potassium, chloride, phosphorus, magnesium, albumin, total bilirubin, gamma-glutamyl transpeptidase (GGT), calcium; and Glomerular Filtration Rate (GFR).
- Urinalysis parameters: amorphous crystals, urine bilirubin, urine blood, calcium oxalate crystals, urine color, urine glucose, urine ketone, urine leukocytes, urine

nitrite, pH, urine protein dipstick, specific gravity, urine urobilinogen, and WBC Casts (Urine) /LPF.

GFR will be calculated using the Schwartz equation at all visits where serum creatinine will be measured (Visits 9, 10, 12, 13 and 15) by the Central Laboratory.

$GFR (mL/min/1.73 m^2) = k[Height (m)]/Serum Creatinine (mg/dL)$ , where  $k=0.41$

Descriptive summary statistics for both baselines, each post-baseline visit, and change from both baselines to each visit will be presented by laboratory test group and core treatment group. Note that if either the baseline or the post-baseline value is missing, then the calculation of change from baseline will also be missing.

Also, shift tables for hematology and serum chemistry will be provided in order to compare a patient's baseline laboratory evaluation relative to each study visit. For the shift tables, the normal laboratory values will be used to evaluate whether a particular laboratory test value is normal, low, or high for each visit value relative to whether or not the baseline value is normal, low, or high. These summaries, including changes from both baselines, will be presented by laboratory test group and core treatment group.

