In addition, summary tables will be presented based on both baselines for the incidence rates of newly occurring clinically notable laboratory abnormalities, where patients will be counted if they have normal or missing baseline value and with at least one post-baseline assessment satisfying the clinically notable criteria. Incidence rates of newly occurring hypocalcemia (based on central lab) by visit will be summarized similarly for patients who have normal or missing baseline level of serum calcium and clinically notable abnormal serum calcium level at each scheduled post-baseline visit. The definition of clinically notable laboratory abnormalities can be found in Appendix section "Clinically notable laboratory values and vital signs" in the protocol.

Furthermore, summary tables will be provided for the number and percentage of patients with liver enzyme abnormalities by each study visit and with at least one post-baseline assessment satisfying the liver enzyme abnormalities compared against both baselines.

Listings of all laboratory parameter measurements will be displayed. The abnormal value will be flagged, e.g., L/H for a value being below/above normal range, and the lower and upper limit of normal values will be presented as well. Central lab calcium values will also be listed for patients with at least one post-baseline laboratory signal of hypocalcemia and the below normal serum calcium results will be flagged as L.

For each numerical laboratory parameter, the number of decimal places to be used for laboratory values should be the same as that for the normal range. For continuous variables recorded as *<lower limit>*, these will be imputed as being half of the lower limit.

All laboratory parameters will be expressed using SI units.

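### Counting a missing baseline as normal could report pre-existing laboratory abnormalities as new, with GGT and total bilirubin the most exposed markers

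*SAP*

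**What the plan says.** The SAP section on laboratory parameters states that "summary tables will be presented based on both baselines for the incidence rates of newly occurring clinically notable laboratory abnormalities". The counting rule is that "patients will be counted if they have normal or missing baseline value and with at least one post-baseline assessment satisfying the clinically notable criteria". The by-visit table of newly occurring hypocalcemia uses the same normal-or-missing condition.

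The same section handles a missing baseline differently for change scores: "if either the baseline or the post-baseline value is missing, then the calculation of change from baseline will also be missing".

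In the Protocol, the Amendment 3 rationale explains that AST and ALT are often raised by muscle breakdown in Duchenne muscular dystrophy, "hence total bilirubin and gamma-glutamyl transpeptidase (GGT) have been added as additional markers to detect any potential liver toxicity". The amendment is described as written "to reflect the changes in the Core protocol (CZOL446H2337) v05". Its status note, dated 10 May 2016, reads: "Twelve (12) patients have been enrolled onto this study, all were enrolled into Group 1".

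Group 1 pre-infusion values come largely from Core samples. Protocol section 3.1 says "Central labs from Visit 8 will be utilized for the Extension Visit 9", subject to a 30-day limit. If there is no extension assessment on or before the first extension infusion, the SAP baseline definition says that "the last assessment in core study will be used instead".

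**The concern.** A patient with no baseline value gives no information on whether a later abnormal value is new. The rule nevertheless counts that patient as a new case, so the error runs in one direction only.

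Scattered gaps in an established test would make this a minor matter. It is more serious for a test introduced partway through, because every patient who passed the baseline visit before testing began is missing the value for the same reason. Amendment 3 suggests that GGT and total bilirubin are such tests, and it gives their purpose as detecting liver toxicity where AST and ALT are hard to read.

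Safety is the primary objective. Protocol section 9.4.1 bases the safety assessment mainly on adverse events and on counts of laboratory values outside set ranges. In a small descriptive study, one or two spurious new cases of a liver marker could alter how the table is read.

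**Working it through.** The plan states no figure to reproduce. The check is textual, followed by a calculation for scale.

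**1. Does an unchanged abnormality qualify?** Yes. Protocol Appendix 1 (Table 13-1) makes any GGT or total bilirubin value outside the normal range notable, with no change from baseline required. The blood pressure and heart rate criteria in the same table differ: they need a normal baseline and a minimum change. A long-standing abnormal GGT therefore qualifies at its first measurement.

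**2. Who could lack a core baseline?** The SAP defines core baseline as the last value on or before the first Core infusion. All 12 patients had passed that point before entering the extension, and so before 10 May 2016. If the two markers were not measured then, none of the 12 has a core baseline. The same holds for any later Group 1 patient already past Core Visit 1 when Core testing began. The summaries of Amendments 1 and 2 mention neither marker, but the Core panel and the date of Core v05 are not in the documents.

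**3. Who could lack an extension baseline?** At most the 12, plus any patient enrolled after 10 May 2016 but before the site implemented the amendment. Some of these may have a value through the fallback to the last Core assessment.

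**4. Who among them can be counted?** Only a patient with a later notable value. Protocol Appendix 7 limits the Visit 10 and 13 samples to creatinine, urea, electrolytes, calcium, magnesium and phosphorus. The later GGT and bilirubin results therefore come from the full chemistry at Visits 12 and 15. A patient who finished before testing began cannot be counted.

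**5. Scale.** Let k be the patients with no baseline and a later test, p the proportion with a pre-existing abnormality that persists, and N the Group 1 size. Then:

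- expected false new cases = k × p
- chance of at least one = 1 − (1 − p)^k
- points added to the incidence = 100 × k × p / N

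The value k = 12 is from the Amendment 3 status note and assumes that all 12 are affected; k = 4 shows a smaller case. The documents do not give p or N. The plan's figure of about 100 covers Groups 1 and 2 together, so N = 40 to 100 is assumed.

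| k | p (assumed) | Expected false new cases, per marker | Chance of at least one | Points added, N = 100 | Points added, N = 40 |
|---|---|---|---|---|---|
| 12 | 5% | 12 × 0.05 = 0.6 | 1 − 0.95^12 = 46% | 0.6 | 1.5 |
| 12 | 10% | 12 × 0.10 = 1.2 | 1 − 0.90^12 = 72% | 1.2 | 3.0 |
| 12 | 20% | 12 × 0.20 = 2.4 | 1 − 0.80^12 = 93% | 2.4 | 6.0 |
| 4 | 5% | 4 × 0.05 = 0.2 | 1 − 0.95^4 = 19% | 0.2 | 0.5 |
| 4 | 20% | 4 × 0.20 = 0.8 | 1 − 0.80^4 = 59% | 0.8 | 2.0 |

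**The case against.** The strongest objection is that no document shows a single missing GGT or bilirubin baseline. The Core panel is not supplied, Core v05 may predate Amendment 3, and the word added stands in a list that largely concerns eligibility. This stands. It means that the number affected cannot be stated, but it does not remove the defect in the rule.

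A second objection is that the rule is cautious: it can over-count but cannot hide a new abnormality, whereas restricting the count to observed baselines would drop genuine new events in patients without one. That is a fair defence for sporadic gaps. A separate row for missing-baseline patients answers it, because every such event is still shown.

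Third, the damage is contained. Change from baseline is set to missing, all values are listed and flagged, the SAP plans separate liver enzyme tables, and this table carries no test. All of this stands. The listings let a careful reader trace a first-ever abnormal value, but the summary table would still call it new.

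A reader might go further and infer that at least 12 of about 100 patients lack a baseline. The documents do not support that. The missing values are an inference, 12 is not a floor on miscounted patients because a later notable value is needed, and 100 includes Group 2, which the SAP's safety set does not cover.

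**Conclusion.** The rule as written can label a pre-existing abnormality as newly occurring, and it can only push the incidence up. GGT and total bilirubin carry a systematic risk if they were not measured before Amendment 3 and Core v05. On the assumptions that all 12 early patients lacked a baseline and were tested later, and that 5–20% had a persisting abnormality, the excess is 0.6 to 2.4 cases per marker. With fewer affected patients it is smaller. For the core baseline it could be larger, by an amount that the documents do not allow anyone to compute.

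Two further inferences should be resisted. A raised count would not by itself show that testing, rather than zoledronic acid, was the cause: the table simply cannot separate the two for these patients. Nor is there reason to expect a bias between core arms, since the rule is the same in both and nothing suggests that missingness depends on the arm. The point is worth correcting before the tables are produced, but it does not undermine the safety analysis as a whole.

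**What to change.** - For each laboratory parameter and each baseline, count a newly occurring notable abnormality only among patients with an observed, non-notable baseline, and use that number as the stated denominator. For GGT and bilirubin, non-notable and normal are the same thing.
- Show patients with a missing baseline and a later notable value in a separate row.
- Apply the same split to the by-visit hypocalcemia table.
- Footnote when GGT and total bilirubin collection began in the Core and in the extension.

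The core-baseline table can stay; dropping it for these two markers is a matter of preference and is not needed once the separate row exists. The cost is a sentence in the SAP, one table row and a footnote. The downside is a slightly smaller denominator: up to 12 of the patients enrolled by 10 May 2016 would leave the extension-baseline GGT and bilirubin counts. The number leaving the core-baseline counts cannot be derived from the documents.

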9.6 Sample size calculation

Participation in the Extension study will be available to all patients completing the Core study CZOL446H2337 and also for the patients who were not eligible to be enrolled to the Core study due to clinically significant back pain from vertebral fracture. Approximately 100 patients in total will be enrolled into the Extension study. Patient recruitment in Group 2 will stop once randomization in the Core study is completed.

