		13 yrs/male	(50.0, 84.0)	If within the normal range at baseline, a value outside of normal range along with at least a 15 unit change
		14 yrs/male	(50.0, 85.0)	If within the normal range at baseline, a value outside of normal range along with at least a 15 unit change
		15 yrs/male	(50.0, 86.0)	If within the normal range at baseline, a value outside of normal range along with at least a 15 unit change
		16 yrs/male	(50.0, 87.0)	If within the normal range at baseline, a value outside of normal range along with at least a 15 unit change
		17-20 yrs/male	(50.0, 89.0)	If within the normal range at baseline, a value outside of normal range along with at least a 15 unit change
		12 yrs/female	(50.0, 82.0)	If within the normal range at baseline, a value outside of normal range along with at least a 15 unit change
		13 yrs/female	(50.0, 84.0)	If within the normal range at baseline, a value outside of normal range along with at least a 15 unit change

Laboratory parameter	Units	Age/gender range	Normal range	Criteria for clinically significant change
		14 yrs/female	(50.0, 85.0)	If within the normal range at baseline, a value outside of normal range along with at least a 15 unit change
		15 yrs/female	(50.0, 86.0)	If within the normal range at baseline, a value outside of normal range along with at least a 15 unit change
		16 yrs/female	(50.0, 86.0)	If within the normal range at baseline, a value outside of normal range along with at least a 15 unit change
		17-20 yrs/ female	(50.0, 86.0)	If within the normal range at baseline, a value outside of normal range along with at least a 15 unit change
Heart Rate	bpm	< 12 yrs	(70.0, 130.0)	If within the normal range at baseline, a value outside of normal range along with at least a 15 unit change
		≥ 12 yrs	(50.0, 120.0)	If within the normal range at baseline, a value outside of normal range along with at least a 15 unit change
Clinical Chemistry				
Blood Urea Nitrogen (serum urea)	mg/dL	≤ 20 yrs	(4.0, 24.0)	Outside the normal range
Calcium	mg/dl	> 2 - 20 yrs	(8.4, 10.3)	Outside the normal range
Chloride	mEq/L	≤ 20 yrs	(94.0, 112.0)	Outside the normal range
Creatinine	mg/dl	5 - 7 yrs/ Female	(0.2, 0.5)	Outside the normal range
		> 7- 10 yrs/ Female	(0.2, 0.6)	Outside the normal range
		> 10 - 13 yrs/ Female	(0.3, 0.7)	Outside the normal range
		> 13 - 16 yrs/ Female	(0.4, 0.8)	Outside the normal range
		> 16 - 20 yrs/ Female	(0.5, 0.9)	Outside the normal range
		5 - 7 yrs/ Male	(0.2, 0.5)	Outside the normal range

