		> 7- 10 yrs/ Male	(0.3, 0.6)	Outside the normal range
		> 10 - 13 yrs/ Male	(0.3, 0.7)	Outside the normal range
> 13 - 16 yrs/ Male	(0.4, 0.8)	Outside the normal range		

Laboratory parameter	Units	Age/gender range	Normal range	Criteria for clinically significant change		
Magnesium	mg/dl	> 16 - 20 yrs/ Male	(0.5, 0.9)	Outside the normal range		
		5 - 7 yrs/ Female	(1.7, 2.2)	Clinically significantly low, if < 1.0 mg/dL		
		> 7- 10 yrs/ Female	(1.6, 2.2)	Clinically significantly low, if < 1.0 mg/dL		
		> 10 - 13 yrs/ Female	(1.6, 2.2)	Clinically significantly low, if < 1.0 mg/dL		
		> 13 - 16 yrs/ Female	(1.6, 2.3)	Clinically significantly low, if < 1.0 mg/dL		
		> 16 - 20 yrs/ Female	(1.5, 2.2)	Clinically significantly low, if < 1.0 mg/dL		
		5 - 7 yrs/ Male	(1.7, 2.4)	Clinically significantly low, if < 1.0 mg/dL		
		> 7- 10 yrs/ Male	(1.6, 2.2)	Clinically significantly low, if < 1.0 mg/dL		
		> 10 - 13 yrs/ Male	(1.6, 2.2)	Clinically significantly low, if < 1.0 mg/dL		
		> 13 - 16 yrs/ Male	(1.6, 2.3)	Clinically significantly low, if < 1.0 mg/dL		
		> 16 - 20 yrs/ Male	(1.5, 2.2)	Clinically significantly low, if < 1.0 mg/dL		
		Potassium	mEq/L	> 1 - 20 yrs	(3.4, 5.4)	Outside the normal range
Phosphorus	mg/dl	5 - 10 yrs	(3.2, 6.1)	Outside the normal range		
		> 10 - 15 yrs	(3.1, 6.0)	Outside the normal range		
		> 15 - 20 yrs	(2.2, 5.1)	Outside the normal range		
		Sodium	mEq/L	≤ 20 yrs	(132.0, 147.0)	Outside the normal range
ALT	U/L	5- 20 yrs	(6 , 200)	Outside the normal range		
AST	U/L	5- 20 yrs	(10 , 200)	Outside the normal range		
Alkaline Phosphatase	U/L	5- 20 yrs	(51 , 315)	Outside the normal range		
Albumin	g/dL	5- 20 yrs	(2.9 – 4.7)	Outside the normal range		
GGT	U/L	5 – 10 yrs/ Female	(0, 24)	Outside the normal range		
		10 – 18 yrs/ Female	(0, 33)	Outside the normal range		
		18 – 20 yrs/ Female	(4, 49)	Outside the normal range		
		5 – 10 yrs/ Male	(0, 24)	Outside the normal range		
		10 – 18 yrs/ Male	(0, 51)	Outside the normal range		
		18 – 20 yrs/ Male	(10, 61)	Outside the normal range		
		Total bilirubin	µmol/L	5 - 20 yrs	(3, 21)	Outside the normal range
		Hematology				

Laboratory parameter	Units	Age/gender range	Normal range	Criteria for clinically significant change
Hemoglobin	g/dl	5 - 12 yrs/ Female	(11.2, 15.5)	Outside the normal range
		> 12 - 20 yrs/ Female	(11.6, 16.4)	Outside the normal range
		5 - 12 yrs/ Male	(11.2, 15.5)	Outside the normal range
		> 12 - 20 yrs/ Male	(12.7, 18.1)	Outside the normal range

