### **Hypocalcemia adverse events and laboratory events**

Hypocalcemia adverse events will be searched based on preferred term and summarized. Patients with reported laboratory measurements associated with a signal of hypocalcemia will be summarized by visit. Lab hypocalcemia (low serum calcium levels) is present if the value of serum calcium from central lab is less than the lower limit of normal range provided by the central lab.

The number and percentage of patients who met these criteria will be summarized by core treatment group and overall.

The hazard ratio, 95% CI and p-value based on a Cox proportional hazards model with core treatment and underlying condition treated with glucocorticoids (stratification factor) as explanatory variables will be presented. Meanwhile, to aid in the assessment that the treatment differences are not inconsistent across the strata, the treatment-by-stratification interaction term will be added to the model described above. P-value for the interaction term will be reported. If a patient experiences a hypocalcemia and low calcium value based on the central lab, the event time is defined as the earlier of these events. Otherwise, a patient is considered censored at the last contact date. Kaplan-Meier estimates will be plotted over time if at least 10% of overall population has experienced the event.

Patient listings will be provided for all adverse events associated with hypocalcemia.

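### Read literally, the SAP's by-visit table of newly occurring hypocalcaemia counts calcium above 10.3 mg/dL as a case, because its criterion is two-sided (minor wording error)

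*SAP*

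**What the plan says.** Four pieces of text bear on this table.

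- **The table (SAP, Laboratory parameters).** "Incidence rates of newly occurring hypocalcemia (based on central lab) by visit will be summarized similarly". The word similarly points back to the preceding general table of newly occurring clinically notable abnormalities. The case rule then given is: "patients who have normal or missing baseline level of serum calcium and clinically notable abnormal serum calcium level at each scheduled post-baseline visit". It states no direction.
- **The cross-reference (same section).** "The definition of clinically notable laboratory abnormalities can be found in Appendix section" on clinically notable values in the protocol. In protocol Appendix 1, Table 13-1, the calcium row for ages above 2 to 20 years gives a normal range of 8.4 to 10.3 mg/dL and the criterion "Outside the normal range".
- **The definition (SAP, Hypocalcemia adverse events and laboratory events).** Laboratory hypocalcaemia is present when central-laboratory serum calcium is "less than the lower limit of normal range provided by the central lab".
- **The listing (SAP, Laboratory parameters).** For children with at least one post-baseline laboratory signal of hypocalcaemia, "the below normal serum calcium results will be flagged as L".

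Table 13-1 states a direction where it wants one. Its magnesium rows read "Clinically significantly low, if < 1.0 mg/dL". The calcium row has no such wording.

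**The concern.** The table carries the name of a one-sided event, but its case rule leads to a two-sided criterion. A programmer who follows the cross-reference would count high calcium as hypocalcaemia.

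Safety is the primary objective. Hypocalcaemia after infusion is a risk the protocol singles out: the Amendment 3 rationale records the data monitoring committee's concern about it, and section 5.1.2 adds calcium supplementation around each infusion because of it. At stake is a by-visit incidence that mixes opposite events. A child counted only for a high value would appear in this table but would be missing from the SAP's own low-calcium summary and, without a low value at another visit, from the hypocalcaemia listing.

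**Working it through.** The documents give no expected rate of low or high calcium, so there is no planned figure to reproduce.

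**Step 1. Apply both written rules to test values.** Rule A is the table's rule combined with Appendix 1: below 8.4 or above 10.3 mg/dL. Rule B is the SAP's definition of laboratory hypocalcaemia: below the central laboratory's lower limit. I take that limit as 8.4; Appendix 1 attributes its ranges to a laboratory, so the two lower limits may well be the same. Baseline is taken as normal or missing.

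| Post-baseline calcium (mg/dL) | Rule A | Rule B |
|---|---|---|
| 8.3 | case | case |
| 8.4 | no | no |
| 9.3 | no | no |
| 10.3 | no | no |
| 10.4 | case | no |
| 11.0 | case | no |

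The rules agree at every value up to 10.3 and disagree at every value above it.

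**Step 2. Illustrate the size at one visit.** Assumption, not in the documents: calcium is normally distributed and 8.4 to 10.3 is a central 95% range, so the limits lie at ±1.96 SD. Let s be the shift in mean calcium in SD units, negative for a fall.

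- Low: P(low) = Φ(−1.96 − s)
- High: P(high) = 1 − Φ(1.96 − s)
- Rule A counts P(low) + P(high); Rule B counts P(low). The miscount is P(high).

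| Shift s | Low-only, per 100 | High (miscount), per 100 | Two-sided, per 100 | Two-sided / low-only |
|---|---|---|---|---|
| 0 | 2.5 | 2.5 | 5.0 | 2.00 |
| −0.25 | 4.4 | 1.4 | 5.7 | 1.31 |
| −0.5 | 7.2 | 0.7 | 7.9 | 1.10 |
| −1.0 | 16.9 | 0.15 | 17.0 | 1.01 |

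If the upper tail is instead taken as 1%, the no-shift miscount is 1.0 per 100.

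**Step 3. Allow for the baseline condition.** The table excludes children whose baseline calcium was abnormal. Step 2 ignores this, which amounts to treating the later value as independent of baseline. At the other extreme, if each child's calcium is fully correlated over time, a child above 10.3 mg/dL later was also above it at baseline and is excluded. Only children with a missing baseline could then be miscounted, so the figure is near 0. Missing baselines should be few, because the SAP's baseline definition falls back on the last Core assessment when no extension value exists.

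**Step 4. Scale.** The protocol states "Approximately 100 patients in total will be enrolled into the Extension study", counting Groups 1 and 2 together. The SAP's analysis sets contain only children who completed the Core study, so the denominator may be below 100. The results are best read as rates per 100.

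**The case against.** The strongest defence is that the SAP should be read as a whole. The table is named for hypocalcaemia, the SAP defines laboratory hypocalcaemia as low calcium, and the related listing flags low values only. A value that is both hypocalcaemic and clinically notable is simply one below the lower limit, so a careful programmer would arrive at the low-only rule. This stands as evidence of intent: nothing suggests that the sponsor means to count high calcium. It does not rescue the sentence, because the criterion it states is two-sided and only the table's name implies otherwise.

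The defence also rightly limits the consequences. The low-calcium summary by visit and the Cox analysis use low values only. The shift tables separate low, normal and high, and the general laboratory listings flag low and high separately. No test, threshold or stopping rule is attached to this table.

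Three stronger readings are tempting but not supported:

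- **Accumulating over visits.** With a 2.5% upper tail at Visits 10, 12, 13 and 15, independence would give 1 − 0.975⁴ = 9.6% of children ever counted on a high value. The table is planned by visit, so this figure describes an output that the sentence does not request.
- **Treating any disagreement between the two hypocalcaemia summaries as an error.** Only this table conditions on baseline status. Its counts may differ from the other summary even under one low-only definition.
- **Inferring that high values will be common because children take calcium and vitamin D.** Section 5.1.2 requires intake at recommended minimum allowances, and the documents give no frequency of high calcium.

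**Conclusion.** The concern holds as a minor error in a stated rule. The written criterion is two-sided, and it conflicts with the SAP's own low-only definition for every calcium value above 10.3 mg/dL.

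The size cannot be established from the documents. Under the assumed central 95% range, the miscount is up to about 2.5 per 100 children per visit with no shift in mean calcium, where it doubles the low-only rate. It becomes negligible if mean calcium falls by 1 SD, and is near 0 if values are fully correlated with baseline. An upward shift would raise it, but the documents give no basis for assuming one. The inflation is therefore largest where calcium is not lowered, and smallest where the drug lowers calcium most.

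A reader might infer that the primary safety conclusion is compromised. It is not: the effect is confined to one descriptive table, and other planned outputs separate low from high calcium.

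**What to change.** In the SAP section Laboratory parameters, in the sentence on newly occurring hypocalcaemia, replace the clinically notable criterion with *serum calcium below the central laboratory's lower limit of normal, as defined for lab hypocalcemia*. Keep the condition that baseline calcium is normal or missing.

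High calcium needs no new output. It remains in the general table of newly occurring clinically notable abnormalities and in the shift tables; a separate table of high calcium is optional.

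The cost is one SAP sentence and one line in the table program. No new data are needed, and no other analysis changes.
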